**Table 2: Weight goals by baseline nutritional status.**

Baseline BMI	Self-reported weight change since diagnosis	Weight goal during study	Calorie Goals/day
<25	Positive or negative	+1 kg/month	Deficit +235 Kcal
25≤30	<5% of body weight lost	+0.5 kg/month	Deficit +117.5 Kcal
25≤30	>5% of body weight lost	+1 kg/month	Deficit +235 Kcal
30-35	<5% of body weight lost	Weight Stability	Deficit +0 Kcal
30-35	>5% of body weight lost	+0.5 kg/month	Deficit +117.5 Kcal
>35	Positive or Negative	Weight Stability	Deficit + 0 Kcal

### **5.1.2 E-Health Nutritional Counseling**

Participants in the e-Health arm will receive the same nutritional goals as above from the research RD using the e-Health application interface. Each participant will be asked to enter 4 days of dietary intake and 2 home weights every 2 weeks. The application will prompt them to enter their data automatically, and the research RD will receive notification of any missing data. The research RD will have access to the e-Health App data and will be able to modify the dietary recommendations made by the application according to the recorded weights using the same guideline as in Table 2.

### **5.1.3 Standard Care**

The standard care group will receive routine nutritional counseling by a treating physician or nurse about the importance of avoiding weight loss at regular clinic visits, as is the standard of care in our Neurology clinics. All participants will be asked to complete and bring with them 4-day food records to each clinic visit.

## **5.2 Compliance with Dietary Recommendations (Adherence Assessment)**

The treating RDs will monitor weight and dietary intake either using paper food diaries every 2-4 weeks (in-person arm) or using the self-reported dietary intake using the e-Health app to verify dietary compliance. Compliance will be defined as greater than 80% data entry using either the paper or electronic food diaries and consuming > 90% of the recommended diet.

### ***5.3 Monitoring of Weight***

Weight will be assessed at every clinic visit in all three groups. Participants in both intervention arms will be asked to weigh themselves at home or in a clinic or allied health professional office every 2-4 weeks and either enter their weights into the e-Health app or in to their Self-Weighing Log. Participants in the in-person arm will be instructed to report significant weight changes by phone to their clinic RD. The clinic RD may modify the dietary recommendations at any time based on observed weight loss, adverse events, or at their discretion. Persistent weight loss despite >90% dietary compliance will prompt an increase in target calories by 235 Kcal/day, or more if the weight loss is more than 0.5 kg/week. Changes in the dietary recommendations will be recorded in the EDC.

Any weight loss >1.5 kg during the study will prompt an increase in the frequency of telephone contact and an appropriate increase in the recommended caloric goals. In addition, any report of weight loss will prompt the treating dietitian to explore (by telephone) whether this is due to unwillingness to continue participation in the trial, inability to comply with the prescribed diet (due to weakness, dysphagia, or dependence on caregivers), or inadequate caloric recommendations. Reported dysphagia (using the swallow screening questionnaire, Appendix 9) will prompt the treating RD to refer the patient for an early in-person evaluation by their medical providers. Participants who lose more than 3 kg despite non-invasive attempts to maintain body weight will be referred to a Speech Language Pathologist for evaluation of dysphagia and possible consideration of a feeding tube.

All participants who require a feeding tube during the study will be prescribed enteral nutrition based upon results of the High Fat/High Calorie diet study. Jevity 1.5 will be prescribed at 1.5 times their calculated TDEE using the HB equation, adjusted for a self-reported activity factor [39]. Given the safety and tolerability results of this study, we do not feel that it is ethical to use a control or eucaloric diet in the standard care arm.

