## **Interventions and Duration**

### **Administration of Intervention**

The goal of the two intervention arms (medical nutrition therapy using in-person counseling or using the e-Health Application) will be modest weight gain of 0.5-1 kg/month. Participants in the in-person nutritional counseling arm will receive an initial face-to-face nutrition counseling session according to a resource book outlining the general nutritional recommendations (see Appendix 1), as well as a personalized nutrition plan with daily caloric goals. They will then receive telephone monitoring of weight with additional telephone counseling as needed between return clinic visits. Home self-reported weights in both intervention arms will be verified at routine clinic visits. Patients in the in-person counseling arm will also receive in-person nutritional counseling at every clinic visit.

Participants in the e-Health arm will receive dietary guidance from the treating RD at the baseline visit including instruction in the completion of food records and weight monitoring using the e-Health App. They will be asked to enter their dietary intake and home weights every 2 weeks. The treating RD will also have access to the e-Health App data and will be able to modify the dietary recommendations of the application according to the recorded weights.

The standard care group will receive routine nutritional counseling by a treating physician or nurse about the importance of avoiding weight loss at regular clinic visits, as is the standard of care in our Neurology clinics.

A research coordinator will collect data on adverse events, disease progression, appetite and quality of life measures in all participants, including standard care participants at month 1 by telephone and at every clinic visit, approximately every 3 months. If participants are unable to make it to the clinic, the above measures will be collected by telephone interview. The total duration of the interventions will be 6 months.

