**Table 1. Schedule of Activities**

Schedule of Activities	Screening/ Baseline	2 week Automatic Alerts	Telephone Visits (every 2-4 weeks)	In-Person Visits (3 and 6 months +/- 1 month)
All Participant Groups including Standard Care				
Written Informed Consent	X			
Abbreviated History/Weight history	X			
MGH Swallow Screening Tool	X			X
Inclusion/Exclusion review	X			
Adverse Events			X 	X*
Vital Signs including Height, Weight	X			X
Clinical Laboratory Assessments	X 			X 
Disease-specific rating scales (ALSFRS-R, UDysRS, UHDRS)	X*			X*
PROMIS SF v1.1	X*			X*
CNAQ	X*			X*
Dietary Intake using 24 hour recall	X			
Dietary Intake using 4 day food records	X			X
DXA Scan (optional)	X			X (month 6 only)
In-Person Nutritional Counseling				
Nutritional Counseling per Protocol	X		X	X*
Dietary Intake using 4 day food records			X (by fax)	
Weight	X		X†	X
e-Health Application Arm				
4 days of Dietary Intake using the e-Health App	X	X		
Weight (2 days)	X	X†		X

 Adverse events and changes in concomitant medications will be obtained by the research coordinator telephone interview in all participants 1 month after the start of the study, including the Standard Care arm. Adverse events will also be captured at every telephone contact by the Registered Dietitian in the In-Person Nutritional Counseling arm.

 Screening labs to include basic chemistry, liver function tests, lipid panel, thyroid stimulating hormone (TSH), uric acid, albumin, and exploratory labs including leptin, PYY and ghrelin.

 Routine Safety labs to include basic chemistry, liver function tests, lipid panel, albumin and hemoglobin A1c. Six month labs will also include exploratory labs (leptin, PYY and ghrelin).

 Labs drawn within 4 weeks of visit for clinical or research purposes may be used for the study

\* May be administered or obtained by telephone within 1 week of the scheduled in-person visit if participants are unable to come to the clinic or too fatigued to complete during their clinic visit. If participants are unable to come to clinic, a self-reported home weight will be obtained and marked as self-reported.

† Participants will weigh themselves at home following specific instructions.

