#### **6.1.2 Telephone Visits (Every 2-4 weeks)**

The Research Coordinator on the study will contact all participants by telephone at month 1 in all arms to determine if there have been any adverse events. The Coordinator will also contact participants by telephone who are unable to return to the clinic for their routine clinic visits, in order to perform disease-related outcome measures and the quality of life questionnaire.

After the initial screening/baseline visit, the treating Registered Dietitian will monitor dietary intake and weight in the in-person arms every 2-4 weeks as necessary based upon observed weight changes. They will monitor dietary compliance by having participants complete paper food records and faxing them along with the Self-Weighing Log for review. They will then contact participants by telephone to query any weight loss or emergence of adverse events. If the treating RD identifies weight loss despite >90% compliance with dietary recommendations, they will adjust their dietary recommendations to meet the target weight from Table 2. They will then contact the study participant at least once every 2 weeks until the participant's weight has stabilized or increased. The frequency and duration of counseling sessions will be documented in the EDC.

The RD in the e-Health Application arm will contact participants who report weight loss through the App directly, through email, or by telephone if necessary. The RD will assess whether the weight loss is due to an inability to comply with the prescribed diet (due to weakness, dysphagia, or dependence on caregivers), versus inadequate caloric recommendations. Symptoms of dysphagia using the self-reported swallow screening questionnaire will prompt the treating RD to refer the patient to SLP for an early in-person evaluation.

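### When a month 3 or 6 visit is done by telephone, the supplied text schedules no swallow check in place of the MGH-SST, and sections 5.3 and 6.1.2 refer a positive self-report to different clinicians

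*Protocol*

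**What the plan says.** The MGH-SST is the plan's swallowing gate. Section 6.1.1 requires a score of at least 5 for entry. It sends those who score lower to an SLP and has their physician and nurse told. Section 6.1.3 repeats the screen for all participants at the month 3 and 6 clinic visits and requires SLP referral before a participant with dysphagia continues. Under sections 6.1.3 and 8, the SLP's finding that swallowing is unsafe is what suspends the study diet or nutritional goals.

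For missed visits, the asterisk footnote to Table 1 begins: "May be administered or obtained by telephone within 1 week of the scheduled in-person visit". It also covers weight: "If participants are unable to come to clinic, a self-reported home weight will be obtained and marked as self-reported". The Précis lists adverse events, progression, appetite and quality of life, and adds: "If participants are unable to make it to the clinic, the above measures will be collected by telephone interview". Section 6.1.2 has the coordinator telephone those who cannot attend "in order to perform disease-related outcome measures and the quality of life questionnaire".

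Between visits there is a self-reported swallowing questionnaire (Appendix 9). Under section 5.3 a positive report "will prompt the treating RD to refer the patient for an early in-person evaluation by their medical providers". Under the e-Health paragraph of section 6.1.2 it "will prompt the treating RD to refer the patient to SLP for an early in-person evaluation".

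**The concern.** Both intervention arms coach most participants to eat more by mouth, in diseases where swallowing can worsen over six months. The plan handles that risk with a repeated screen tied to SLP review. If a visit moves to the telephone, counseling can go on while the scheduled screen drops out. It drops out for the people least able to come in, because the footnote is written for those who cannot attend or are too fatigued.

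The second issue is that a dietitian who receives a positive self-report finds two different instructions. Since suspension of the nutritional goals depends on the SLP, it matters whether the report must reach one. What is at stake is participant safety monitoring. The SAP does not touch the point.

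**Working it through.** The plan gives no figure to reproduce, so the check is mainly a comparison of texts.

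**Step 1. What may be done by telephone (Table 1, months 3 and 6).**

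| Item | Telephone asterisk? | Substitute named? |
|---|---|---|
| MGH-SST | No | None |
| Clinic weight | No | Self-reported home weight |
| Adverse events | Yes | Not needed |
| Disease rating scales, PROMIS, CNAQ | Yes | Not needed |
| "Nutritional Counseling per Protocol" (in-person arm) | Yes | Not needed |

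Counseling can therefore proceed by telephone, and the swallow screen cannot. The footnote deals with weight, which also lacks an asterisk, but not with swallowing.

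**Step 2. What the calls contain.** The Précis list and the coordinator's missed-visit call in section 6.1.2 name no swallow check. The in-person-arm dietitian calls (every 2 to 4 weeks, section 6.1.2) ask about weight loss and adverse events. Appendix 9 has no row in Table 1 and no stated timing in the supplied text.

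**Step 3. What other routes exist.**
- Any reported weight loss leads the dietitian to ask why by telephone, with dysphagia among the causes to consider (section 5.3).
- Loss of more than 3 kg leads to SLP referral (section 5.3).
- Voluntary complaints are recorded at each in-person and telephone visit (section 10.5). The same section says that symptoms of disease progression are not recorded as adverse events.

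The first two need weight loss, so a participant whose weight holds or rises starts neither. The third needs the participant to raise the problem. None is a scheduled swallow screen.

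**Step 4. Referral of a positive self-report.** Section 5.3, which applies to both counseling arms, names the medical providers. Section 6.1.2 names the SLP. That sentence sits in the e-Health paragraph but speaks of the treating RD, the term the preceding paragraph uses for the in-person arm's dietitian. The in-person paragraph has no dysphagia referral of its own. On a narrow reading, the e-Health arm has two rules and the in-person arm only the one in 5.3. On a broad reading, both arms have two rules. The sections disagree either way.

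**Step 5. Interval between screens.** Inputs are visits at months 3 and 6, each +/- 1 month (Table 1), and a 6-month intervention.
- Month 3 attended: 3 - 0 = 3 months from the baseline screen (2 to 4 with the window).
- Month 3 by telephone, with no in-person screen within its window: 6 - 0 = 6 months (5 to 7 with the window).
- Ratio: 6 / 3 = 2. The next screen then falls at about the end of the intervention.

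A missed month 6 screen matters less, because the intervention ends then.

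**The case against.** The strongest objection is that the documents which could settle the matter are not available. Appendix 9, the app specifications (Appendix 4) or the rating-scale forms might set a timing or ask about swallowing, and the scales are telephone-permitted. This stands in part. A reader might infer that a telephone visit involves no swallowing enquiry at all, and the supplied text cannot show that. It does show that no answer given on a scale is tied to a referral.

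Second, the missing asterisk may mean that the screen stays due in person within the +/- 1 month window. That is possible, but nothing requires a return visit after a telephone one.

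Third, a reader might infer that positive reports in the in-person arm do not reach the SLP. The documents do not support this. Section 6.1.2 may cover that arm, and under 5.3 the medical providers must see the patient early and in person and are free to involve the SLP. Triage by a clinician is a defensible choice. What remains is that the protocol states two choices.

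Fourth, with 150 ALS participants in three equal arms, a reader might take 150 / 3 = 50 per counseling arm as the number affected. That figure counts everyone under a rule. Being missed would take an unattended visit, new dysphagia, no reported weight loss and no complaint, in someone who passed the entry screen. The documents quantify none of these.

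**Conclusion.** The point holds in limited form. On the supplied text, a participant whose visit is done by telephone loses the scheduled MGH-SST, with no scheduled swallow check linked to a referral in its place, while in-person-arm counseling may continue. Separately, sections 5.3 and 6.1.2 name different referral targets for the same finding, and the reach of 6.1.2 is unclear.

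The only size that can be given is the interval: nominally 6 months instead of 3 when month 3 is done by telephone. This assumes no later in-person screen within the window and no timing set in an appendix that was not supplied. The number of people affected cannot be derived.

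A reader might go further and infer biased weight results or a particular rate of harm. Nothing in the documents supports either. This is a safety-monitoring improvement of low to moderate priority, worth making because it is cheap.

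**What to change.** 1. Add Appendix 9 to Table 1 for any participant, in any arm, whose month 3 or month 6 visit is done by telephone. The coordinator asks it on the missed-visit call already in section 6.1.2.
2. State the hand-off. The coordinator passes a positive result to the treating RD in the counseling arms, or to the treating physician or nurse in standard care.
3. Use one rule in section 5.3 and in both dietitian paragraphs of section 6.1.2: a positive report in either counseling arm leads to SLP referral, with the medical providers informed. This is consistent with sections 6.1.1 and 6.1.3.
4. Keep the referral above 3 kg lost as a separate trigger. Do not add a calorie freeze while the SLP review is pending. It would conflict with the weight-loss response in sections 5.3 and 7, and 5.3 already lets the dietitian adjust recommendations at their discretion.

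The cost is one Table 1 row and a few sentences, using a questionnaire, a call and a specialist already in the plan. The downside is some extra SLP referrals, which the documents do not allow to be counted. If Appendix 4 or 9 already fixes the timing for missed visits, a cross-reference in Table 1 can replace the timing in item 1. The hand-off and the single referral rule are still needed.

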### ***5.4 Concomitant Medications***

Throughout the study, investigators may prescribe any other concomitant medications or treatments deemed necessary to provide adequate supportive care. All concomitant medications received by a subject will be recorded on the appropriate source documents and in the Electronic Data Capture (EDC) System.

#### ***5.4.1 Exclusionary Medications***

None. Due to the low risk of the study, investigational medications will also be allowed during the trial.

## **6. Study Activities**

### **6.1 Study Visits**

#### **6.1.1 Screening/Baseline Visit and Informed Consent**

A schedule of activities for each intervention is provided in **Table 1**. At the screening visit, subjects will provide informed consent. Informed consent may be obtained by physicians, research nurses or study coordinators with IRB approval to consent participants in the study. No procedures will be done prior to consent. Participants will be asked basic demographic questions and will be asked for contact information for their caregivers. Participants will provide basic information about their diagnosis and disease history, such as date of diagnosis and site of symptom onset. Participants will be screened for dysphagia using the MGH Swallow Screening Tool (MGH SST) and must score at least a 5 in order to enroll (in order to ensure that they will be able to comply for 6 months with an oral diet). Participants who score below a 5 on the MGH-SST will be referred to a SLP and their treating physician and nurse will be informed. Participants who pass the MGH-SST will then be weighed and asked questions about the degree of weight loss they may have experienced since before their illness (weight loss may predate their diagnosis). Once all inclusion criteria have been met, all participants will be randomized into one of the three study arms.

Additional study activities may be completed within 2 weeks of the screening/baseline visit if participants are unable to complete the activities at that time. All participants will complete a 24 hour recall. Participants in the two intervention arms will then receive written instructions with their calculated caloric goals and general dietary recommendations. Participants in the e-Health App arm who do not have access to an iPhone or iPad will be provided an iPad for the duration of the study free of cost. They will then be trained and will enter their randomization codes into the application in order to access their caloric goals and recommendations. The research RD will maintain a list linking the identification codes of the participants to their contact information. Participants will also have their blood drawn for the research and safety laboratory studies including a urine pregnancy test for participants who have consented for the optional DXA study. Participants who have had safety labs drawn for routine clinical (or research purposes) within 4 weeks may have their laboratory data used for the study rather than repeating the labs. Finally, participants will be given a Self Weighing Log (Appendix 1) and told to weigh themselves at least every 2-4 weeks using the log and to contact the site if they lose 3 or more pounds.

Participants who consent to the optional DXA study will be invited to go to the MGH CRC at their convenience for the DXA exam. All women of child-bearing potential will undergo a urine pregnancy test immediately prior to the DXA exam. The timing of this exam can occur within 14 days of the baseline visit.

#### **6.1.2 Telephone Visits (Every 2-4 weeks)**

The Research Coordinator on the study will contact all participants by telephone at month 1 in all arms to determine if there have been any adverse events. The Coordinator will also contact participants by telephone who are unable to return to the clinic for their routine clinic visits, in order to perform disease-related outcome measures and the quality of life questionnaire.

After the initial screening/baseline visit, the treating Registered Dietitian will monitor dietary intake and weight in the in-person arms every 2-4 weeks as necessary based upon observed weight changes. They will monitor dietary compliance by having participants complete paper food records and faxing them along with the Self-Weighing Log for review. They will then contact participants by telephone to query any weight loss or emergence of adverse events. If the treating RD identifies weight loss despite >90% compliance with dietary recommendations, they will adjust their dietary recommendations to meet the target weight from Table 2. They will then contact the study participant at least once every 2 weeks until the participant's weight has stabilized or increased. The frequency and duration of counseling sessions will be documented in the EDC.

The RD in the e-Health Application arm will contact participants who report weight loss through the App directly, through email, or by telephone if necessary. The RD will assess whether the weight loss is due to an inability to comply with the prescribed diet (due to weakness, dysphagia, or dependence on caregivers), versus inadequate caloric recommendations. Symptoms of dysphagia using the self-reported swallow screening questionnaire will prompt the treating RD to refer the patient to SLP for an early in-person evaluation.

